4.6 Early Withdrawal of Subjects

4.6.1 When and How to Withdraw Subjects

A subject may be withdrawn from the study prior to that subject completing all of the study related procedures for the following reasons.

- Unanticipated adverse effects that are possibly or probably related to the study drug
- patients who miss more than 20% of doses or are not adherent to protocol requirements.
- Disease progression
- Subject decision to withdraw from the study (withdrawal of consent)
- Liver transplantation

Subjects who withdraw from the study for safety concerns or disease progression will be included in the primary analysis (safety and tolerability). As this is a short-term study, there will be no specific clinical follow-up for subjects withdrawn from the study.

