8.2 Sample Size, Effect Size, and Power Calculations

Our primary endpoint is change in A-a gradient over 6 months between the treatment and placebo groups. We expect 20 patients to enroll in this study. We have set $\alpha = 0.05$ and the standard deviation of change in AaPO₂ at ~ 10 mmHg. Assuming all this, we will have an 80% power to detect a 13.2 mmHg change in A-a gradient.

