8.4 Statistical Methods

8.4.1 Data Analysis

The intent-to-treat analysis will include all randomized subjects. Hypothesis testing will use two-sided α level 0.05 without correction for multiplicity. We will summarize demographics and baseline and follow-up endpoints.

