8.4.4 Survival Analysis

A log-rank statistic will be used to compare time to death, although there are expected to be few events.

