9.3.3 Interpretation of Definitions

AE Reporting Period

The study period during which AEs must be reported is normally defined as the period from the initiation of any study procedures to the end of the study treatment follow-up. For this study, the end of study treatment follow-up is Week 14.

Pre-existing Condition

A pre-existing condition is one that is present at the start of the study. A pre-existing condition should be recorded as an AE if the frequency, intensity, or the character of the condition worsens during the study period.

General Physical Examination Findings

At screening, any clinically significant abnormality should be recorded as a pre-existing condition. At the end of the study, any new clinically significant findings/abnormalities that meet the definition of an AE must also be recorded and documented as an AE.

Post-Study AE

All unresolved AEs considered possibly, probably or definitely related to the study drug should be followed by the investigator until the events are resolved, the subject is lost to follow-up, or the AE is otherwise explained. At the last scheduled visit, the investigator should instruct each subject to report any subsequent event(s) that the subject, or the subject's personal physician, believes might reasonably be related to participation in this study. The investigator should notify the study sponsor of any death or AE occurring at any time after a subject has discontinued or terminated study participation that may reasonably be related to this study. The sponsor should also be notified if the investigator should become aware of the development of cancer or of a congenital anomaly in a subsequently conceived offspring of a subject that has participated in this study.

Abnormal Laboratory Values

A clinical laboratory abnormality should be documented as an AE if any one of the following conditions is met:

- The laboratory abnormality is considered clinically significant by the local PI and is not otherwise refuted by a repeat test to confirm the abnormality
- The abnormality suggests a disease and/or organ toxicity
- The abnormality is of a degree that requires active management; e.g. change of dose, discontinuation of the drug, more frequent follow-up assessments, further diagnostic investigation, etc.

Hospitalization, Prolonged Hospitalization or Surgery

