9.7 Confidentiality of Study Data

Information about study subjects will be kept confidential and managed according to the requirements of the Health Insurance Portability and Accountability Act of 1996 (HIPAA). Those regulations require a signed subject authorization informing the subject of the following:

- What protected health information (PHI) will be collected from subjects in this study
- Who will have access to that information and why
- Who will use or disclose that information
- The rights of a research subject to revoke their authorization for use of their PHI.

In the event that a subject revokes authorization to collect or use PHI, the investigator, by regulation, retains the ability to use all information collected prior to the revocation of subject authorization. For subjects that have revoked authorization to collect or use PHI, attempts should be made to obtain permission to collect at least vital status (long term survival status that the subject is alive) at the end of their scheduled study period.

10 Quality Control and Data Handling

Design strategies and monitoring activities throughout the study will ensure the integrity and high quality of the data. Design strategies include randomization of treatment assignment, masking, and training and certification of personnel. The rigorous monitoring program includes data queries and performance monitoring over the time of the trial.

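### Time to death is compared between arms, but no section requires all-cause vital status at 6 months for every randomised subject, and the sections on follow-up after withdrawal conflict

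*Combined protocol and SAP*

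**What the plan says.** **The analysis.** Section 8.4.4 reads, in full: "A log-rank statistic will be used to compare time to death, although there are expected to be few events". It gives no population, time horizon or censoring rule. The only general statement on population is in 8.4.1: "The intent-to-treat analysis will include all randomized subjects".

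**Follow-up after withdrawal.**
- Section 4.6.1 lists reasons for leaving the study early: drug-related adverse effects, more than 20% of doses missed, disease progression, withdrawn consent and liver transplantation. It then says that "there will be no specific clinical follow-up for subjects withdrawn from the study".
- Section 4.6.2 says that follow-up or survival data on such subjects may be important, and matter to the integrity of the final analysis. Its only commitment is to seek permission where consent is withdrawn.
- Sections 8.4.5 and 9.4 keep subjects who stop study drug on the scheduled assessments. Section 9.4 does so expressly to protect the intent-to-treat analysis. It also takes out of both treatment and procedures anyone who withdraws consent for both.
- Section 9.7, for subjects who revoke authorization, says "attempts should be made to obtain permission to collect at least vital status" at the end of the scheduled study period.

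**Safety reporting.** Section 9.3.3 closes the adverse event reporting period at Week 14. After participation ends, it asks for the sponsor to be told about "any death or AE occurring at any time after a subject has discontinued or terminated study participation that may reasonably be related to this study". Section 9.3.4 asks for serious and unexpected events to go to the coordinating centre whether or not they are related.

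**The concern.** A log-rank test of time to death needs the same information on every subject: dead by the cut-off, with a date, or known alive at it. Here the rule that applies depends on how a subject left. Someone who only stops study drug stays in follow-up. Someone classed as withdrawn from the study may have no further contact. Because 8.4.5 uses the information available up to the end of follow-up, that subject would be censored on departure.

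Two of the listed reasons for leaving, disease progression and adverse effects, plausibly go with a higher risk of death. Censoring at departure may then be informative, and the comparison could be biased if departures differ between arms. In what 8.5 calls the first study of letrozole for this indication, a complete death count also matters as plain safety information.

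**Working it through.** **The plan's own power figure.** The documents give no event count or power for the log-rank test, so there is nothing to reproduce there. The one stated figure is for the primary endpoint: "we will have an 80% power to detect a 13.2 mmHg change in A-a gradient", with "the standard deviation of change in AaPO₂ at ~ 10 mmHg" (8.2) and "Hypothesis testing will use two-sided α level 0.05 without correction for multiplicity" (8.4.1). With 10 per arm and d = 13.2/10 = 1.32, a two-sided two-sample t-test (noncentral t) has power 79.7%. The stated 80% is reproduced, and this point does not touch it.

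**Who is covered for all-cause death to month 6?**

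| Subject's status | Governing text | All-cause death captured? |
|---|---|---|
| Stops drug, stays in study | 8.4.5, 9.4 | Yes, through scheduled visits |
| Withdrawn from study for progression, adverse effects or missed doses | 4.6.1 against 4.6.2, 8.4.5, 9.4 | Unclear; the sections conflict |
| Withdraws consent | 4.6.2 | Only if permission is obtained |
| Revokes authorization | 9.7 | Only if permission is obtained |
| Lost to follow-up | 8.4.5 | No; data used to last contact |

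The safety routes add little. The 9.3.3 notice carries a relatedness condition. The 9.3.4 route does not, but it needs the event to be unexpected. Section 9.3.2 calls an event expected if it is known to go with the condition under study, so most deaths from liver disease or HPS would not qualify. Section 9.3.4 also does not say whether it applies after withdrawal.

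**How many deaths could fall after departure?** All inputs here are assumptions. Six-month mortality of 5-20% gives 20 x 0.05 = 1 to 20 x 0.20 = 4 deaths. Suppose 20% of subjects leave at month 3 and have h times the death rate of the others. The share of deaths after departure is then approximately 0.2 x 0.5h / (0.8 + 0.2h) = 0.1h / (0.8 + 0.2h):
- h = 1: 0.1/1.0 = 10%
- h = 3: 0.3/1.4 = 21%
- h = 5: 0.5/1.8 = 28%

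That is 1 x 0.10 = 0.1 to 4 x 0.28 = 1.1 deaths, or about one at most. With equal hazards (h = 1) and 10-30% leaving at mid-study, each leaver's risk afterwards is q = 1 - sqrt(1 - m), where m is 6-month mortality. For m = 0.05 and 2 leavers, the expected number is 2 x 0.025 = 0.05 and the chance of at least one is 5%. For m = 0.20 and 6 leavers, they are 6 x 0.106 = 0.63 and 49%.

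**What does one missed death do?** Take 10 per arm and deaths at months 2.5, 3.5, 4.5 and 5.5, all in one arm (assumed). The statistic is (O - E)^2 / V, where E is the sum of p, V is the sum of p(1 - p), and p is that arm's share of those at risk at each death.
- All four counted: E = 10/20 + 9/19 + 8/18 + 7/17 = 1.830, V = 0.988, chi-square = (4 - 1.830)^2/0.988 = 4.76, p = 0.029.
- One later death missed, subject censored at month 3: E = 10/20 + 8/18 + 7/17 = 1.356, V = 0.739, chi-square = 3.66, p = 0.056.
- One missed, subject censored at month 2: E = 9/19 + 8/18 + 7/17 = 1.330, V = 0.738, chi-square = 3.78, p = 0.052.

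**How much can the test show anyway?** With 1 to 4 deaths, Schoenfeld power is about 5-10% for a hazard ratio of 2 and 8-20% for a hazard ratio of 3. Reaching 80% power for a hazard ratio of 2 would take 66 deaths, more than the 20 subjects enrolled.

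**The case against.** The strongest reply is that the plan already means to follow people. Sections 8.4.5 and 9.4 keep those who stop treatment on schedule, 4.6.2 recognises the value of survival data, and 4.6.2 and 9.7 seek permission after consent or authorization is withdrawn. Under 9.4, subjects who worsen clinically stay on their assigned medication, and under 4.6.1 progression is only a possible reason for withdrawal. On that view only those who refuse all contact, or are lost, are at risk, and no wording recovers the refusals. Much of this stands: the exposed group is small. But 4.6.1 still withdraws some subjects from the study itself and gives them no specific follow-up, and no text says which section prevails.

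Three stronger readings are tempting and are not supported.
- A reader might infer from 9.3.3 that deaths enter the mortality analysis only if judged related. That sentence governs post-study safety notices to the sponsor. It does not define the outcome data.
- A reader might illustrate the harm by losing two of three or two of four deaths (p from 0.067 to 0.264, or from 0.029 to 0.112). The shares above imply about one at most.
- A reader might infer that a death behind a missing month-6 AaPO2 would be hidden. Section 10.4 requires missing data to be explained, and 9.4 requires the reason for withdrawal in the CRF.

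It is also fair to object that the 4 v 0 example needs 40% mortality in one arm and none in the other, and that it rests on a large-sample approximation. Fisher's exact test gives p = 0.087 for 4 v 0 before any death is missed. The example shows sensitivity to a single event and does not forecast a result.

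**Conclusion.** The point holds, at minor severity. The plan compares time to death but does not require all-cause vital status to a fixed date for every randomised subject. Section 4.6.1 cannot be read together with 4.6.2, 8.4.5 and 9.4 without a choice that the plan does not make. Subjects who leave the study can be censored at departure, possibly informatively.

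That the comparison covers all randomised subjects is inferred from 8.4.1, since 8.4.4 names no population. The sizes rest on assumed mortality, withdrawal and hazard inputs that the documents do not give. Whether there is bias, and in which direction, cannot be known in advance. It would need departure to be linked to risk of death, with a pattern that differs by arm.

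Mortality is not among the primary or secondary endpoints in 3.4, 3.5 or 7.2, the plan itself expects few events, and the test has little power. A reader might infer a threat to the trial's main result, but the documents do not support that: the AaPO2 comparison does not use these data.

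**What to change.** - **4.6.2:** replace the permissive wording with a requirement to obtain all-cause vital status, and the date of any death, at 6 months after randomisation for all 20 randomised subjects. Use clinical records or a telephone call, and except only subjects who refuse permission.
- **8.4.4:** state that the comparison includes all randomised subjects, runs to 6 months after randomisation, and censors a subject only at the last date known alive.
- **4.6.1, 4.6.2, 8.4.5 and 9.4:** reconcile these sections so that each way of leaving treatment or the study leads to one stated follow-up rule. The Week 14 end of adverse event reporting in 9.3.3 should be reconciled with the 6-month study period at the same time.

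The 9.3.3 safety notice can stay as it is, because vital status would be collected as outcome data. The cost is a few sentences, plus a record check or a call for the few subjects who leave early. Sample size, visits for subjects who remain, and the primary analysis do not change.

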9.3.4 Reporting Procedures for Unanticipated Problems and Adverse Events

Participating investigators should notify the local IRB, in an expedited manner, of those events related to study participation that are unforeseen and indicate that participants or others are at increased risk of harm. Researchers should submit reports of the following problems:

- Any AE or UP (regardless of whether the event is serious or non-serious, on-site or off-site) that occurs any time during or after the research study, which in the opinion of the principal investigator is:
 - 1.) Unexpected (An event is “unexpected” when its specificity and severity are not accurately reflected in the protocol-related documents, such as the IRB-approved research protocol, any applicable investigator brochure, and the current IRB-approved informed consent document and other relevant sources of information, such as product labeling and package inserts.)
AND
 - 2.) Related to the research procedures (An event is “related to the research procedures” if in the opinion of the principal investigator or sponsor, the event was more likely than not to be caused by the research procedures.)
AND

- 3.) suggests that the research places subjects or others at a greater risk of harm (including physical, psychological, economic, or social harm) than was previously known or recognized

Serious and unanticipated AEs which are fatal and indicates that participants or others are at increased risk of harm must be reported within 24 hours to the CCC, as well as to the local IRB per their requirements.

Reporting Process

UPs posing risks to subjects or others as noted above will be reported to the local IRB using the institution required form or as a written report of the event (including a description of the event with information regarding its fulfilment of the above criteria, follow-up/resolution and need for revision to consent form and/or other study documentation).

The participating Investigator is expected to report any serious and unexpected adverse experiences, whether or not they are considered related to the CCC, usually within 24 hours.

The participating Investigator is expected to provide as much of the following information as is available to the CCC:

- Protocol name and number
- Subject identifiers
- Demographic data
- Nature of the event
- Severity of the event
- Probable relationship (causality) of AE to study procedure
- Date and time of AE onset
- Date and time of AE resolution, if available
- Concomitant medications that the participant was taking for an underlying medical condition or disease and the therapeutic agents used for the treatment of the adverse event
- Clinical assessment of participant conducted at time of SAE/AE
- Results of any laboratory and/or diagnostic procedures, and treatment
- Follow-up plan
- Outcome
- Autopsy findings (if appropriate)

The participating Investigator will provide details about the AE to the CCC as they become available. If additional information cannot be obtained for whatever reason, this will be documented. The participating Investigator should inform the CCC when no other information is expected. The participating Investigator should provide the CCC with a logical, complete, and accurate narrative description of the SAE based upon the above information. The participating Investigator should promptly determine an assessment of causality.

The participating Investigator should communicate to the CCC if the IRB requires revisions to the informed consent form or other measures.

The CCC will determine if any corrective actions should be initiated as a result of any known specific or collective SAE/AE(s) and inform all participating Investigators of the corrective action (e.g., revision of informed consent form, protocol, CRF).

The participating Investigator/designee should keep originals or photocopies of all relevant documentation, including facsimile confirmations, and file them in the participant's file.

All participating Investigators should ensure that their sites report all routine AE(s) as part of the periodic or annual reporting requirements to the IRB of record.

The CCC and any participating Investigator should file copies of all correspondence with the IRB in the appropriate section of the Regulatory Master File or site study file.

Other Reportable events:

The following events are also reportable to the IRB:

- Any adverse experience that, even without detailed analysis, represents an unexpected SAE that is rare in the absence of drug exposure (such as agranulocytosis, hepatic necrosis).
- Any AE that would cause a modification to the investigators brochure, protocol or ICF, or would prompt other action by the IRB to assure protection of human subjects.
- Information that indicates a change to the risks or potential benefits of the research, in terms of severity or frequency. For example:
 - An interim analysis indicates that participants have a lower rate of response to treatment than initially expected.
 - Safety monitoring indicates that a particular side effect is more severe, or more frequent than initially expected.
 - A paper is published from another study that shows that an arm of your research study is of no therapeutic value.
- Change in FDA safety labeling or withdrawal from marketing of a drug, device, or biologic used in a research protocol.
- Breach of confidentiality
- Change to the protocol taken without prior IRB review to eliminate apparent immediate hazard to a research participant.
- Incarceration of a participant when the research was not previously approved under Subpart C and the investigator believes it is in the best interest of the subject to remain on the study.
- Complaint of a participant when the complaint indicates unexpected risks or the complaint cannot be resolved by the research team.
- Protocol violation (meaning an accidental or unintentional deviation from the IRB approved protocol) that in the opinion of the investigator placed one or more participants at increased risk, or affects the rights or welfare of subjects.

9.4 Subject Withdrawal

A subject has the right to withdraw from the study entirely at any time for any reason without prejudice to future medical care by the investigator or other physician. The investigator also has

the right to withdraw subjects from the study in the event of concurrent illness, AEs, or other reasons deemed to be in the subject's best interest.

Subjects **must be withdrawn** from the trial (treatment and procedures) for the following reasons:

- Subject withdraws consent for study treatment and study procedures. A subject must be removed from the trial at his/her own request. At any time during the trial and without giving reasons, a subject may decline to participate further. The subject will not suffer any disadvantage as a result.
- Death.

Any subject removed from the trial will remain under medical supervision until discharge or transfer is medically acceptable.

In all cases, the reason for withdrawal must be recorded in the CRF and in the subject's medical records.

In order to preserve the integrity of the intention-to-treat analysis, even if the subject is withdrawn from the treatment portion of the protocol (either due to subject, physician, or investigator decision), it is imperative to continue with the scheduled follow-up assessments both for the safety of the subject and for completeness of data collection. This will be explained to potential subjects at the time of informed consent. The importance of compliance with study visits will be reinforced throughout the trial. If the treatment is permanently withdrawn, the subject will return to the center for safety assessment (history, physical examination, and clinical laboratories, if necessary).

In the event of clinical worsening, subjects will be continued on their assigned study medication. There is no evidence that the medication under study is effective in subjects with HPS, so that there is neither reason to unmask the study therapy nor to initiate treatment with sorafenib in such subjects.

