4.6.2 Data Collection and Follow-up for Withdrawn Subjects

Even though a subject has withdrawn from the study, it may be important to collect some follow-up or survival data on such subjects throughout the protocol defined follow-up period. Such data is important to the integrity of the final study analysis since early withdrawal could be related to the safety profile of the study drug in this population. If a subject withdraws consent to participate in the study, for subject safety reasons, attempts will be made to obtain permission to collect follow up information whenever possible.

5 Study Drug

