5.5 Subject Compliance Monitoring

Compliance will be assessed using pill logs and pill containers. Subjects will be asked to bring bottles to each study visit to allow for tracking of compliance and medication control. Non-compliant patients who miss more than 20% of doses will be asked to withdraw from the study for not complying with study protocol.

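### Section 5.5 asks non-adherent patients to leave the study, against section 9.4, so month-6 blood gases can be lost from a completers-only primary test

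*Combined protocol and SAP*

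**What the plan says.** **Text that keeps assessments going.** Section 9.4 makes removal from both treatment and procedures mandatory only for withdrawn consent or death. For a patient withdrawn from treatment alone it says "it is imperative to continue with the scheduled follow-up assessments both for the safety of the subject and for completeness of data collection", and gives preserving the intention-to-treat analysis as the reason. Section 8.4.5 strongly encourages patients who stop drug to complete all scheduled procedures. Section 8.4.1 puts all randomised subjects in the intent-to-treat analysis, and section 8.6 says all primary analyses are intent-to-treat.

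**Text that can end participation.**
- Section 5.5: "Non-compliant patients who miss more than 20% of doses will be asked to withdraw from the study for not complying with study protocol".
- Section 4.6.1: "A subject may be withdrawn from the study prior to that subject completing all of the study related procedures for the following reasons". The reasons include disease progression, adverse effects thought to be drug-related, and non-adherence ("patients who miss more than 20% of doses or are not adherent to protocol requirements"). It adds: "As this is a short-term study, there will be no specific clinical follow-up for subjects withdrawn from the study".
- Section 9.6.1: patients whose adverse effects are judged probably related to letrozole stop the study.
- Section 9.4 itself gives the investigator a right to withdraw subjects from the study for concurrent illness, adverse events or other reasons.

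**Text in between.** Section 4.6.1 includes safety and progression withdrawals in a primary analysis that it labels safety and tolerability. Section 4.6.2 says "it may be important to collect some follow-up or survival data on such subjects" over the planned follow-up period.

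**Analysis.** Section 8.4.3 makes the primary test a two-sample t-test on the change in AaPO2 from baseline to 6 months. Section 8.4.5 runs it in completers only, with imputation as a sensitivity analysis.

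**The concern.** A t-test on 6-month change cannot use a patient without a month-6 arterial blood gas. Whether that gas is drawn after a patient stops drug depends on which section the site follows. Section 5.5 names the study, not the drug, and tells staff to ask the patient to leave. Section 9.4 wants the same patient to keep attending. No order of precedence is stated, and the two sites could act differently.

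The triggers arise after randomisation. Missed doses, related adverse effects and progression may differ by arm, and some may relate to oxygenation. Losing these patients from the primary test lowers power and, if loss is related to outcome, biases the comparison. The sample size in section 8.2 has no dropout allowance, so the trial has nothing in reserve.

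**Working it through.** **Inputs.** From the documents: 20 patients randomised 1:1 (10 per arm), SD of change about 10 mmHg, two-sided alpha 0.05, difference 13.2 mmHg. Assumed, because the documents do not give them: the number lost, and the correlation r between the tendency to be lost and the change in AaPO2.

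**1. The plan's own figure.** The noncentrality is 13.2 / (10 × √(1/10 + 1/10)) = 2.95, with 18 df and critical value 2.101. Power is 79.7%, against the stated 80%. The figure therefore needs all 20 month-6 values.

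**2. Loss unrelated to outcome (r = 0).** The same formula gives 77.3% for 9 vs 10, 74.8% for 9 vs 9, and 74.3% for 8 vs 10. There is no bias and type I error stays at 5%.

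**3. Loss related to outcome.** In a sample of 10, the two largest standard normal values have expectations 1.539 and 1.001. If the patients with the highest latent loss score leave one arm, the mean of those remaining moves by:
- one lost: r × 10 × 1.539 / 9, which is 0.85 mmHg at r = 0.5 and 1.71 at r = 1
- two lost: r × 10 × (1.539 + 1.001) / 8, which is 1.59 mmHg at r = 0.5 and 3.18 at r = 1

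Simulation (400,000 trials per scenario, pooled t-test) gives the error rates. A higher AaPO2 is worse, so losing worse letrozole patients favours letrozole. Losing better ones reverses the sign.

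| Letrozole patients lost | r | Shift (mmHg) | Type I error | Power, worse leave | Power, better leave |
|---|---|---|---|---|---|
| 1 | 0 | 0 | 5.0% | 77.3% | 77.3% |
| 1 | 0.5 | ±0.85 | 5.5% | 83.0% | 72.9% |
| 1 | 1 (ceiling) | ±1.71 | 7.4% | 89.4% | 69.9% |
| 2 | 0 | 0 | 5.0% | 74.3% | 74.3% |
| 2 | 0.5 | ±1.59 | 6.4% | 84.5% | 65.0% |
| 2 | 1 (ceiling) | ±3.18 | 11.6% | 93.7% | 57.9% |

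For losses from placebo, the two power columns swap. With one lost from each arm at r = 0.5, the shift is zero and type I error is 5.4%.

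**4. Price of keeping patients who are off drug.** Suppose one of the ten letrozole patients stops drug, keeps no effect and is still analysed. The expected difference is 13.2 × 9/10 = 11.88 mmHg, and simulated power is about 68%. If half the effect remains, it is 13.2 × 9.5/10 = 12.54 mmHg and about 75%. Two such patients give about 55% and 70%. With no treatment effect and all 20 values present, type I error stays at 5%.

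**The case against.** Much of the conflict can be read away. Section 4.6.1 is permissive and forces no one out. Its sentence on follow-up can mean clinical care rather than study tests. Stopping the study in section 9.6.1 can mean stopping drug. Section 9.4 keeps worsening patients on drug while section 4.6.1 lists disease progression as a reason to withdraw, but neither term is defined and they need not be the same event. Section 4.6.1 does include safety and progression withdrawals in an analysis, and section 4.6.2 says of data on withdrawn patients: "Such data is important to the integrity of the final study analysis". Section 8.4.5 plans imputation, and section 8.4.3 plans mixed models or GEE for longitudinal secondary outcomes including blood gases, where a patient lost after month 3 still contributes.

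Most of this stands, and it narrows the firm conflict to section 5.5 against section 9.4; the other items are ambiguities. It does not remove the problem. Section 4.6.2 asks only for some data and does not name the month-6 gas. The inclusion sentence in section 4.6.1 concerns safety and tolerability, omits non-adherent patients, and cannot supply a measurement that was never taken. Imputation and longitudinal models leave the primary t-test as it is.

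A reader might go further and infer that the primary result will be biased towards letrozole, or towards whichever arm loses more patients. The documents do not support that. They link neither missed doses nor drug-related adverse effects to worse AaPO2, and the sign reverses if better patients leave.

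**Conclusion.** The point holds as a conflict of wording with a possible effect on the primary test. Followed as written, section 5.5 can remove randomised patients from the AaPO2 comparison, against section 9.4 and the intent-to-treat statements in sections 8.4.1 and 8.6. Sections 4.6.1 and 9.6.1 can be followed the same way but need not be.

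Size and direction are unknown. With one or two patients lost and r no higher than 0.5, the effects are modest: a shift of at most about 1.6 mmHg against a detectable difference of 13.2, type I error between 5.0% and 6.4%, and power between 65% and 84.5%. The 7.4% and 11.6% error rates need perfect correlation and are ceilings, not expectations. All of this rests on the assumed losses, the assumed r and the plan's SD of 10 mmHg. The change should be made, because it is cheap and section 9.4 already states the intended principle.

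**What to change.** 1. In sections 5.5, 4.6.1 and 9.6.1, change withdrawal from, or stopping, the study to discontinuation of study drug for non-adherence, adverse effects and disease progression. Replace the sentence in section 4.6.1 on no specific follow-up with continued scheduled assessments, as in section 9.4.
2. In section 9.4, limit the investigator's right of withdrawal to study drug. State that worsening patients continue drug unless a drug-stopping rule applies.
3. In section 8.4.5, replace the completers-only analysis with all randomised patients who have a month-6 blood gas, analysed as randomised whether or not drug was stopped. Seek that gas from everyone except after death or withdrawn consent. Do not use gases taken after liver transplantation as the month-6 value, because section 7.1.1 says gas exchange normalises then. Treat them as missing in the primary test and in the planned imputation sensitivity analysis.

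**Cost.** Wording in five sections. The month-6 gas is already scheduled, so no visit or test is added, and patients may still leave at any time. The statistical price is dilution. One letrozole patient with no remaining effect gives about 68% power, against about 77% if that patient were lost at random. That is the cost of the intent-to-treat comparison the plan already says it wants, and the protocol should say so.
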